## Time Period and Frequency for Event Assessment and Follow-Up:

Unanticipated problems will be recorded in the data collection system throughout the study.

The PI will record all reportable events occurring during the testing session or reported by the participant to the PI within 30 days of the testing session. If participating in multiple study session, at each study visit, the investigator will inquire about the occurrence of AE/SAEs since the last visit. Events will be followed for outcome information until resolution or stabilization.

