## VAS measures:

Participants will be asked to make the following ratings throughout the session:

Intensity of the touch sensation: "No sensation" (far left) to "Most intense sensation imaginable" (far right)

Unpleasantness of the touch sensation: "Extremely unpleasant" (far left) to "Neutral" (middle) to "Extremely pleasant" (far right)

Pain intensity: "No pain" (far left) to "Most intense pain imaginable" (far right)

Pain unpleasantness: "Extremely unpleasant" (far left) to "Neutral" (middle) to "Extremely pleasant" (far right)

*Skin monitoring*: Photos will be taken of the participant's arm before and after injection to document the possibility of any adverse response. Photos will not show any other part of the body other than the arm and will be deleted from the smartphone the same day as the session and stored on secure computers by subject ID, like our other PII. In the case of an adverse reaction, the study physicians will grade the severity of reaction as advised by the FDA.

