Blood pressure and oxygenation will be monitored before and after OT injection and at approximately 5 minute intervals (BP) or continuously (pulse ox) for the remainder of the session.

**Post-sensory testing:** Perception of pain and gentle brushing will be tested beginning ~10min after injection on the injected arm, given timing of OT effects in prior studies, and then on the control arm. A post-block baseline sensory test will be conducted, identical to the affective sensory testing described above. All testing will be conducted within a ~3-4cm^2 sized region of skin proximate to the injection site on the dorsal forearm. At the end of testing, the injected arm will be observed by a licensed provider to confirm normal sensation and lack of any adverse response to OT injection.

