## Risks and discomforts associated with Oxytocin:

We do not expect any risks from OT injected in the skin beyond possible headache, facial flushing, and sensation of heart pounding. Skin injection of OT has been conducted in only one published human study. In this study subcutaneous injection of 4  $\mu$ g/4 ml OT just prior to surgical incision resulted in more stable hemodynamic parameters during surgery and reduced postsurgical pain. Adverse events were not systematically addressed in this paper, however no gross problems were reported.

Other routes of peripheral and systemic OT administration have demonstrated safety in healthy volunteers. Most clinical reports of intranasal oxytocin fail to mention adverse events or state that no serious or severe adverse events were noted. A few reports provide more detail, including a study of 49 older men (age 73 years; range 65-78) which observed no serious adverse events and no difference between 41µg intranasal OT and placebo , and a pediatric study  and meta-analysis showing no safety signals with prolonged intranasal oxytocin administration for weeks .

For intramuscular (IM) injection of oxytocin, only 1 study has been conducted in non-pregnant/postpartum persons; in these healthy participants, IM injection of 10IU (~17 µg) oxytocin (EVER Neuro Pharma GmbH, Unterach, Austria) in the thigh did not cause any serious adverse events or clinically significant findings for any safety parameters. OT produces no tissue toxicity in these concentrations when injected intravascularly or into the muscle. Based on preliminary studies with intravenous and intranasal administration of oxytocin from the lab of [name] at Wake Forest University, particularly at plasma oxytocin concentrations > 350 pg/ml, the following adverse events may occur: headache; facial flushing; sensation of heart pounding.

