## Risks and discomforts associated with subcutaneous injection:

The main risks of a subcutaneous injection are pain, redness, swelling, itchiness, bruising, or irritation around the site of injection for 1-2 days after injection. Rare complications include infection of the puncture or accidental injection into a blood vessel or nerve This is not expected to increase risk given the demonstrated safety of larger doses of intravenous OT described above.

**Risks and discomforts associated with blood draw (funds permitting for baseline OT assay):** The main risks of drawing blood from a vein include discomfort at the site of puncture, possible bruising and swelling around the puncture site, and (rarely) an infection or faintness from the procedure. Some subjects could experience a vasovagal (fainting) response due to the discomfort of needle insertion or anxiety associated with the procedure.

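### Once participants leave, adverse events are solicited only at a later visit, so about half of oxytocin injections have only volunteered reports after the session

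*Combined protocol and SAP*

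**What the plan says.** Section 15 (Time Period and Frequency for Event Assessment and Follow-Up) gives three routes by which an event enters the record:

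- During the session: "The PI will record all reportable events occurring during the testing session".
- Afterwards, on the participant's initiative: events "reported by the participant to the PI within 30 days of the testing session".
- Afterwards, on the investigator's initiative: "If participating in multiple study session, at each study visit, the investigator will inquire about the occurrence of AE/SAEs since the last visit".

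Section 9 schedules a baseline calibration and two injection sessions, one with oxytocin and one with saline, in randomized order. Baseline and Session 1 share a visit. No visit, call, diary or survey is described after Session 2, or for someone who does not return after Session 1.

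Session 1 (after baseline) and Session 2 each last about an hour. Within them, Section 9 provides blood pressure about every 5 minutes after injection, continuous pulse oximetry, continuous heart-rate recording, and arm photographs before and after injection. It adds a final check: "At the end of testing, the injected arm will be observed by a licensed provider to confirm normal sensation".

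Section 14 places injection-site pain, redness, swelling, itching, bruising or irritation "around the site of injection for 1-2 days after injection". For oxytocin itself it expects no risks "beyond possible headache, facial flushing, and sensation of heart pounding". It also states that only one published human study has used this route, and that adverse events were not systematically addressed there.

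**The concern.** Of the three routes, only the inquiry at a visit actively asks about the time after the participant has gone home, and it needs a later visit. The inquiry at Session 1 comes before any injection, and the one at Session 2 looks back on the Session 1 injection. Nothing looks back on the Session 2 injection. For that injection, and for a Session 1 injection in someone who leaves the study, the 30-day window depends on the participant choosing to report.

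The expected local reactions outlast an hour-long session by a day or more, so in-session checks cannot follow them through. The three named systemic symptoms are at least partly subjective, and no end-of-session question about them is described.

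At stake is how a low event count can be read. The protocol itself notes that the existing human evidence by this route lacks systematic adverse event data. Followed exactly, this plan would leave a similar gap after the session for about half of its own oxytocin exposures.

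**Working it through.** The plan gives no figure for the share of injections with solicited follow-up, so there is none to reproduce. The share has to be derived from the design.

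**Inputs**

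- 20 participants, two sessions each (Section 10, Subject Population).
- One oxytocin and one saline injection per person, in two randomized orders (Section 9, Participant Randomization). I take the orders as equal, 10 and 10.
- Attrition of 25% (Sample Size Determination & Power) or 20% (Participant Randomization). The two sections differ, so both are used. I assume all losses occur after Session 1.
- Sessions more than two days apart, both within 4 months of consent (Timeline).

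**Step 1. Oxytocin injections with no later inquiry.** Let *d* be the fraction lost after Session 1, equal in both orders. Per person randomized:

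- oxytocin injections given = 0.5 + 0.5(1 − d)
- of these, with no later visit = 0.5d (oxytocin first, did not return) + 0.5(1 − d) (oxytocin at Session 2) = 0.5
- share = 0.5 / [0.5 + 0.5(1 − d)] = 1/(2 − d)

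| d | Oxytocin injections (20 randomized) | No later inquiry | Share |
|---|---|---|---|
| 0 | 20 | 10 | 50% |
| 0.20 | 18 | 10 | 56% |
| 0.25 | 17.5 | 10 | 57% |

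The share depends only on *d*. It is the same whether 20 is the number randomized or more are randomized to obtain 20 completers.

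**Step 2. Sensitivity.** If all 5 losses (25% of 20) came from the saline-first order, the share would be 5/15 = 33%. If all came from the oxytocin-first order, it would be 15/20 = 75%. If each sex has its own list of 20 codes, 10 per order, and only 10 are used (an assumption), chance puts 7 to 13 of 20 oxytocin injections at Session 2 (about a 95% range), or 35% to 65%.

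**Step 3. Comparison with saline.** The gap follows session position and order is randomized, so the share for saline is the same in expectation. Without dropout, the solicited data are 10 oxytocin and 10 saline injections, all at Session 1 and in different people. Nobody contributes both.

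**Step 4. What halving the inquiries means.** Suppose a delayed event has true rate *e* and is always disclosed when asked about (both assumptions). The chance of eliciting at least one from *n* people asked is 1 − (1 − e)^n.

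- e = 5%: 40% with n = 10, 64% with n = 20.
- e = 10%: 65% with n = 10, 88% with n = 20.

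With no events elicited, the one-sided 95% upper limit on the rate is 1 − 0.05^(1/n): 26% for n = 10, 14% for n = 20.

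**Step 5. Timing of the one inquiry that exists.** It can come anywhere from just over two days to nearly 4 months after the Session 1 injection. Recall therefore varies between participants, and the inquiry may fall outside the 30-day window.

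**The case against.** The strongest reply is that the trial does watch for harm actively. Every injection has blood pressure, oximetry, heart-rate recording, photographs and a licensed provider's check of the arm. Flushing is visible to staff, and a heart-rate trace bears on palpitations. The DSMB reviews retention and reasons for drop-out (Section 15, Safety Data), so a reaction that made someone withdraw could surface there. Consent pages are not in the text available, and they may tell participants what to report.

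Much of this stands. A reader might infer that half of the oxytocin injections have no active follow-up at all. The documents contradict that: the gap opens only when the participant leaves. Nor can one say that events in dropouts are simply lost. But in-session checks cannot see the following day, a reason for leaving is not an adverse event inquiry, and consent instructions would still produce volunteered reports.

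Three other stronger readings also lack support:

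- **Bias between oxytocin and saline.** Randomized order makes the gap equal in expectation.
- **A failing halting rule.** It needs a related serious event or two severe events. The delayed effects the protocol mainly expects are minor site reactions, and the documents do not show that the rule would be affected.
- **A percentage of events captured.** This needs a volunteered-reporting rate, which the documents do not give.

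**Conclusion.** The point holds for the period after the participant leaves the session. No solicited adverse event inquiry is planned after any Session 2 injection, or after a Session 1 injection in someone who does not return. That is 50% of oxytocin injections with no dropout, and 56% to 57% at the plan's own attrition figures. These shares assume equal orders, losses after Session 1, and equal losses across orders. Extreme one-sided losses at 25% attrition would give 33% to 75%.

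The consequences are under-counting of delayed events in both conditions and no within-person comparison of them. An absence of delayed events in the record would not show that none occurred. The finding concerns safety ascertainment only and does not touch the pain or touch outcomes.

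**What to change.** In Section 15 (Time Period and Frequency for Event Assessment and Follow-Up), add one short solicited adverse event contact, by REDCap survey or call, after every injection. Include Session 2 and participants who do not return. Time it once the 1-2 day local-reaction period given in Section 14 has passed. In Section 9, add a question at the end of each session, oxytocin and saline alike, about headache, flushing and heart pounding, alongside the existing arm check.

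Planned solicited coverage of oxytocin injections would rise from 10 of 20 to 20 of 20 with no dropout, or from 7.5 to 17.5 of 17.5 with 25% lost after Session 1. Both injections would be asked about at a similar interval, which restores the within-person comparison. A further contact at the close of the 30-day window is optional.

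The cost is a protocol amendment, up to two short contacts per completer (one for someone who leaves after Session 1), and a three-item checklist per session. REDCap is already in use for the questionnaires. The downside is slightly more staff and participant time, and a few more minor events recorded.

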## Characteristics of an Adverse Event Relationship to Study Intervention:

To assess relationship of an event to study intervention, the following guidelines are used:

- Related (Possible, Probable, Definite)
  - $\circ$  The event is known to occur with the study intervention.
  - There is a temporal relationship between the intervention and event onset.
  - o The event abates when the intervention is discontinued.
  - $\circ$  The event reappears upon a re-challenge with the intervention.
  - Not Related (Unlikely, Not Related)
    - There is no temporal relationship between the intervention and event onset.
    - An alternate etiology has been established.

## Expectedness of SAEs:

The Study PI and Independent Monitoring Committee will be responsible for determining whether an SAE is expected or unexpected. An adverse event will be considered unexpected if the nature, severity, or frequency of the event is not consistent with the risk information previously described for the intervention.

# Severity of Event:

The following scale will be used to grade adverse events:

- Mild: no intervention required; no impact on activities of daily living (ADL)
- Moderate: minimal, local, or non-invasive intervention indicated; moderate impact on ADL
- Severe: significant symptoms requiring invasive intervention; subject seeks medical attention, needs major assistance with ADL

## **Unanticipated Problem Reporting:**

Incidents or events that meet the OHRP criteria for unanticipated problems require the creation and completion of an unanticipated problem report form. OHRP recommends that investigators include the following information when reporting an adverse event, or any other incident, experience, or outcome as an unanticipated problem to the IRB:

- Appropriate identifying information for the research protocol, such as the title, investigator's name, and the IRB project number;
- A detailed description of the adverse event, incident, experience, or outcome;
- An explanation of the basis for determining that the adverse event, incident, experience, or outcome represents an unanticipated problem;
- A description of any changes to the protocol or other corrective actions that have been taken or are proposed in response to the unanticipated problem.

To satisfy the requirement for prompt reporting, unanticipated problems will be reported using the following timeline:

- Unanticipated problems that are serious adverse events will be reported to the IRB, Independent Safety Monitor(s), and NIH within 7 days of the investigator becoming aware of the event.
- Any other unanticipated problem will be reported to the IRB, Independent Safety Monitor(s), and NIH within 14 days of the investigator becoming aware of the problem.

## Adverse Event Reporting for IND Studies:

SAEs that are unanticipated, serious, and possibly related to the study intervention will be reported to the Independent Monitors(s), IRB, FDA, and NIH in accordance with requirements. For the IND:

- 7-day IND Safety Report (unexpected fatal or life-threatening AEs related to the intervention); a copy of the report sent to the FDA will be submitted to the NIH Program Officer and Independent Safety Monitor(s) within 24 hours of FDA notification.
- 15-day IND Safety Report (any other serious and unexpected AE related to the intervention); a copy of the report submitted to the FDA will be submitted to the NIH Program Officer and Independent Safety Monitor(s) within 24 hours of FDA notification.
- All other AEs documented during the course of the trial will be reported to NIH on an annual basis by way of inclusion in the annual report and in the annual AE summary which will be provided to NIH and to the Independent Monitors. The Independent Safety Monitor(s) Report will state that all AEs have been reviewed.

## Halting Rules:

The study will be halted Halt if any SAE related to study participation or two severe AEs/reactions occur, until a complete safety review is convened.

#### Measurement and Reporting of Subject Accrual:

Review of the rate of subject accrual will occur monthly during the recruitment phase to ensure that a sufficient number of participants are being enrolled, in keeping with proposed recruitment projections, and that they meet eligibility criteria and fulfill the targeted ethnic diversity goals outlined in the grant proposal.

# 16. PRIVACY AND CONFIDENTIALITY CONSIDERATIONS INCLUDING DATA ACCESS AND MANAGEMENT

Study recruitment and enrollment will be monitored through a Screening/Enrollment Log, both created as password protected Microsoft Excel spreadsheets. No identifying information will be used on any study documents after enrollment. Enrolled subjects will be assigned a unique subject identification number (SID) that will be used on all Case Report Forms (CRFs) and study related documents after enrollment. The SID will be linked to subject identifiable information only in the Screening/Enrollment Log, created and password protected in a Microsoft excel spreadsheet. This will be stored on a coordinator's password protected and encrypted computer in the ACTRI.

To minimize possible risk of breach of confidentiality, the SID will be used for each subject as the unique identifier for all research related activities. All information collected, including self-report questionnaires, psychological assessments, and sensory data will be identified solely by the SID and without any personal identifiers. Electronic data will be stored on password protected computers on servers in the ACTRI. Only strictly anonymous data will be entered into electronic databases and used for statistical analysis. Access to the participant numbering system will be limited to the Principal Investigator and the research staff involved in the study. Research files will be kept in locked cabinets or drawers in a locked office or clinic or storage room, in the ACTRI, and made available only to qualified personnel for research purposes. No verbal or written information concerning a subject will be released to anyone without expressed written consent by the subject. Any data shared with the sponsor will be transferred electronically with no identifiers whatsoever.

As part of consent procedures, participants will be advised of precautions taken to preserve confidentiality. Further, all individuals involved in data collection procedures will be instructed to not divulge any information concerning participants to any person or agency without the written and explicit consent of the patients. These procedures have been effective in completely protecting patient information in past studies. All study staff receive Good Clinic Practice and Human Subjects Protection training as well as HIPAA privacy training before working with any participants. No published or presented materials will identify patients by names, initials, or any other means that could be used to identify the participant.

Recruitment will take place from private office and clinic areas. Recruitment will not take place in an open public area, hallways, a crowded waiting room, or other venue that would jeopardize participant privacy. The informed consent process will take place in a private room at the ACTRI where the participant can ask questions without feelings of embarrassment or discomfort.

## **17. POTENTIAL BENEFITS**

There are no direct benefits from participating in this study. Each participant will receive financial compensation for participating in the study, but all participants will be informed that there are no direct benefits to them for participating in the research study.

Study participants may gain satisfaction from the knowledge that they are contributing to a better understanding the neurobehavioral underpinnings of affective touch and pain perception, with potential applications for chronic pain.

## 18. RISK/BENEFIT RATIO

There are no alternative procedures that will provide comparable information to that obtained by the methods described in this study. The risks for this study are small in comparison to the substantial anticipated benefits regarding better understanding of mechanisms of pain and touch perception.

## **19. EXPENSE TO PARTICIPANT**

There will be no expense to the participant except for their transportation.

## 20. COMPENSATION FOR PARTICIPATION

Participants will receive \$80 for the Baseline session, \$60 for Session 2, for a total of \$140. A free parking voucher code will be made available for each study session.

## 23. FUNDING SUPPORT FOR THIS STUDY

An ACTRI Pilot Award application has been submitted for funding consideration.

## 24. BIOLOGICAL MATERIALS TRANSFER AGREEMENT

Not applicable.

## 25. INVESTIGATIONAL DRUG FACT SHEET AND IND/IDE HOLDER

An IND application (sponsor [name] PhD) has been submitted to the FDA for subcutaneous injection of oxytocin for research purposes. An investigational drug fact sheet is appended.

#### **26. IMPACT ON STAFF**

Not applicable.

#### **27. CONFLICT OF INTEREST**

The PI and all key personnel report no conflicts of interest.

#### 28. SUPPLEMENTAL INSTRUCTIONS FOR CANCER-RELATED STUDIES

Not applicable.

#### 29. OTHER APPROVALS/REGULATED MATERIALS

Not applicable.

#### 30. PROCEDURES FOR SURROGATE CONSENT AND/OR DECISIONAL CAPACITY ASSESSMENT

Those trained to screen subjects will be responsible for determining the decisional capacity of the subjects being considered for inclusion in the protocol. During the consent process, those screening subjects will reiterate study details and will assess for an understanding of the required study involvement. These details include the nature of pain tasks, the duration of study, and maximum and partial compensation. If the decisional capacity is questionable, further evaluation will be performed and documented in regard to this matter. If the investigator determines that the subject lacks decision-making capacity, they will not enroll the subject into the study.
